### **9.3.3 Type and Duration of the Follow-up of Subjects After Adverse Events**

AEs and SAEs will be followed until resolution or stability even if this extends beyond the study reporting period. Resolution is defined as when the condition resolves (either with or without residual effects), returns to baseline for a pre-existing condition or has stabilized and is expected to remain chronic.

## **9.4 Individual Halting Rules**

Enrolled subjects will not be eligible to receive placebo microneedle patches 2/3 placement at Day 8 (+2 days) if any of the following occur:

- An ongoing  $\geq$ Grade 1 local site reaction (see Appendix B).
- An ongoing  $\geq$ Grade 1 solicited general AE (see Appendix C) or unsolicited AE.

Subjects unable to receive placebo microneedle patches 2/3 due to meeting an individual halting rule will continue to follow up according to the protocol through Day 27 – 38.

## 9.5 Study Halting Rules

Further enrollment and placebo microneedle patch application (e.g., placebo microneedle patch 2/3 placement) to subjects will be halted if any of the following occur:

- Any death following placebo microneedle patch application.
- Any subject develops erosion, ulceration, or abscess at the administration site related to study product administration.
- Any subject develops laryngospasm, bronchospasm or anaphylaxis within 24 hours of placebo microneedle patch administration.
- Any subject experiences a placebo microneedle patch-related SAE.
- Any Grade 3 AEs or an SAE that cannot be clearly attributed to another cause.

If the study is halted, the site will immediately notify the Sponsor and the Emory IRB. Prior to recommencing enrollment, all available safety data will be reviewed by the site Investigator and the Sponsor.

## 10 CLINICAL MONITORING STRUCTURE

### 10.1 Study Documentation

The Principal Investigator will maintain appropriate medical and research records for this trial, in compliance with ICH-GCP, regulatory and institutional requirements for the protection of confidentiality of subjects. Source documents are the original data source used by the Investigator that allow verification of the study data collected, captured on CRFs and entered into the study database. Source documents may include but are not limited to: clinical charts and progress notes, memoranda, pharmacy dispensing records and other research records maintained for the clinical trial. Study CRFs may serve as the original source document.

The Investigator will permit authorized representatives of the Sponsor and regulatory agencies to examine (and when required by applicable law, to copy) clinical records for the purposes of quality assurance reviews, audits and evaluation of the study safety and progress.

### 10.2 Data Collection and Data Management

The Investigator and designated study staff will keep accurate records to ensure that the conduct of the study is fully documented. The investigator will ensure that all CRFs and subject study files are legible and complete for every subject. A detailed description of each of the forms and the procedures required for forms completion and submission can be found in the MOP. The Investigator or designee must record all required subject data, and an explanation must be documented for any missing data.

Clinical research data will be collected and recorded in a timely fashion in a secure electronic web-based database (e.g., REDCap). Extracted data will be sent to the statisticians for statistical analysis as needed. The final study database and statistical evaluations will be transferred to the Sponsor at the study completion.

### 10.3 Data Quality Control/Quality Assurance

The Principal Investigator, through the use of an internal Quality Management Plan and appropriate internal site monitoring staff, will be responsible for the regular review of the conduct of the trial, for verifying adherence to the protocol, and for confirming the completeness,

consistency, and accuracy of all documented data and accuracy of source documentation verification.

## **10.4 Site Monitoring Plan**

The study data integrity and compliance with the protocol will be assured by the monitoring of the study documentation and study conduct by an internal monitor. Routine data monitoring and protocol compliance will be performed by the site investigators, study coordinator and quality assurance staff on an ongoing basis. The study clinical monitoring plan and the data quality monitoring plan will be developed and followed by the study site.

## **10.5 Timing/Reports**

A cumulative report of related AE grade 3, major deviations and subject terminations is sent to sponsor on a monthly basis. SAEs are reported within 24 hours to the IRB and the sponsor.

## **10.6 Study Records Retention**

Study records including source documentation, CRFs, informed consent documents, laboratory report forms, study product accountability records and regulatory files will be retained for a period of 18 years after the submission of the final report and closeout procedures on the research project for which the clinical trials records were prepared or termination of the study, unless a longer retention period is specified by Emory policy, the sponsor, or regulation. In addition, records must be maintained for at least 2 years after a marketing application is approved for the study product (i.e. microneedle patch). The Investigator must notify the study Sponsor prior to destroying any study records. Consent forms for future use samples must be maintained as long as the sample exists.

## **10.7 Protocol Deviations**

A protocol deviation is any change, deviation or departure from the study design or procedures of the research protocol that is not approved by the Sponsor and/or IRB prior to its initiation or implementation, or deviation from standard operating procedures, Good Clinical Practices (GCPs), federal state or local regulations. These protocol violations may be major or

minor violations. The Investigator and study staff will have ongoing monitoring to identify any protocol deviations during the conduct of the study and to report any deviations to the Sponsor or Emory IRB as appropriate.

Minor protocol deviations are deviations from the research protocol that do not (a) adversely affect the rights, welfare or safety of subjects; (b) adversely affect the integrity of research data; (c) adversely affect the subjects' willingness to continue participation in the research; or (d) were not undertaken to prevent immediate hazard to a human subject. A minor protocol deviation or protocol non-compliance will be reported to the Sponsor on an ongoing basis. Minor deviations do not require reporting to the Emory IRB for review unless subject safety is a concern. A major protocol deviation must be reported to the Sponsor and Emory IRB (per IRB reporting guidelines) immediately upon discovery of the deviation and no later than 10 days after site awareness.

## 11 STATISTICAL CONSIDERATIONS

### 11.1 Study Outcome Endpoints

#### Primary:

##### Safety:

- Occurrence of placebo microneedle patch-related serious adverse events from Day 1 through the Final Study Visit (Day 27 – 38).
- Occurrence of Grade 3 placebo microneedle patch-related solicited adverse events for the 8 days following application of the patch.

##### Reactogenicity:

- Occurrence of solicited application site reactogenicity (e.g., erythema, induration, bruising, itching) for the 8 days following application of the patch.

#### Secondary:

- Occurrence of Grade 3 placebo microneedle patch-related unsolicited adverse events from Day 1 through the Final Study Visit (Day 27 – 38).
- Occurrence of new-onset medical conditions (NOMC) from Day 1 through the Final Study Visit (Day 27 – 38).
- Occurrence of solicited and unsolicited adverse events described at the site at which the placebo microneedle patch was applied.
- Quantitative and qualitative description of LAR responses to survey questions.

### 11.2 Sample Size Considerations

For sample size calculation and statistical analysis plan the primary and secondary endpoints will mainly be addressed. The small numbers in this study allow only rough estimates of safety. With 25 subjects per cohort, if the true event rate is 5%, we will have 34% chance to observe one AE and 12% chance to observe more. If the true event rate is 10%, the chance to observe one AE is 38%, and the chance to observe more than one AEs is 34%.

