Infants and children will be enrolled by sequential age groups using an age de-escalation approach (Table 1). At least 4 infants or children from each Group must complete Day 8 without halting criteria having been met (as detailed in Section 9.5) before subjects will be enrolled into the next younger age group within a Cohort. For Cohort 1, at least the first 2 children in each Group will have the microneedle patch applied to the skin overlying the shoulder blade. If this site is well tolerated without halting criteria having been met (as detailed in Section 9.5), additional microneedle patches may be applied at a different location on the same participant and in subsequent participants to the upper arm, forearm, wrist, thigh, shin, and/or foot. For Cohort 2, microneedle patches may be applied to the

shoulder blade, upper arm, forearm, wrist, thigh, shin, and/or foot. If the first site is well tolerated in the first two children without halting criteria having been met (as detailed in Section 9.5), additional microneedle patches may be applied to the same participants and in subsequent participants.

Table 1: Cohorts and Groups of Enrolled Infants and Young Children			
Cohort	Group Age Range*	Number **	Study Product (administered Day 1 and possibly Day 8)
1	12 – 24 months	Up to 7	Microneedle formulation 1
1	5 – 11 months	Up to 6	Microneedle formulation 1
1	6 weeks – 4 months	Up to 12	Microneedle formulation 1
2	12 – 24 months	Up to 12	Microneedle formulation 2
2	5 – 11 months	Up to 12	Microneedle formulation 2
2	6 weeks – 4 months	Up to 12	Microneedle formulation 2

*\*All age ranges are inclusive. 4 children from each age group must complete Day 8 without halting criteria having been met (as detailed in Section 9.5) before subjects will be enrolled into the next younger age group.*

*\*\* Total number enrolled into each Cohort will be ≤25.*

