### 11.3 Analysis Plan

The safety population includes all subjects who receive the placebo microneedle patch. The safety population will be the primary analysis population for safety analyses. AEs will be analyzed using the safety population. Subjects will be analyzed as treated.

Primary Outcome Endpoints

AEs, reactogenicity events and SAEs will be recorded throughout the study. AEs will be coded using the Medical Dictionary for Regulatory Activities (MedDRA) dictionary. AE summary tables will be based on treatment-emergent AEs for the safety population. Descriptive statistics (e.g., number and percentage of subjects) will be used for each treatment group. AEs will be summarized by severity, relationship to treatment, and AEs leading to discontinuation. SAEs will also be tabulated by overall and treatment related events.

Secondary Outcome Endpoints

Unsolicited AEs and new-onset medical conditions (NOMC) will be recorded. AEs will be coded using the Medical Dictionary for Regulatory Activities (MedDRA) dictionary. AE summary tables will be based on treatment-emergent AEs for the safety population. Descriptive statistics (e.g., number and percentage of subjects) will be used for each treatment group. AEs will be summarized by severity, relationship to treatment, and AEs leading to discontinuation. NOMC will also be tabulated by overall and treatment related events.

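### Section 11.2 names 25 subjects per cohort, but its probabilities of observing adverse events are those of 12 subjects and understate the chance of seeing an event

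*Combined protocol and SAP*

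**What the plan says.** Section 11.2 opens with a caution, "The small numbers in this study allow only rough estimates of safety", and then gives two scenarios for a cohort of 25.

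- At a true rate of 5%: "With 25 subjects per cohort, if the true event rate is 5%, we will have 34% chance to observe one AE and 12% chance" of more than one.
- At a true rate of 10%: "the chance to observe one AE is 38%, and the chance to observe more than one AEs is 34" per cent.

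The footnote to Table 1 (Section 4, repeated in the Protocol Summary) makes 25 the upper limit: "Total number enrolled into each Cohort will be ≤25". Within the cohorts, Table 1 allows up to 12 subjects in four of the six age groups. The other two, both in Cohort 1, allow up to 7 and up to 6.

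Section 11.3 plans no hypothesis test. For both primary and secondary endpoints it states: "Descriptive statistics (e.g., number and percentage of subjects) will be used for each treatment group".

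**The concern.** At a 10% rate, 25 subjects are expected to yield 25 × 0.10 = 2.5 subjects with an event. With that expectation, a single event should not be more likely than several, yet the text gives 38% for one and 34% for more than one. Likewise, at a 5% rate the expected count is 1.25, and a 12% chance of more than one is too low.

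These four percentages are the only quantitative content of the sample size section. Safety and reactogenicity form the primary objective and the analysis is descriptive, so this is the one place that tells a reader how to weigh a cohort with few or no events. If the figures belong to a different sample size, the plan misstates what its own design can show.

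**Working it through.** **Inputs.** Cohort size n = 25 and true event rates p = 5% and 10%, all from Section 11.2. Each subject either has the event or does not, independently and with the same probability. This is the usual model for such statements; the text does not name one.

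**Formulas.**

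- No event: P(0) = (1 − p)^n
- Exactly one: P(1) = n · p · (1 − p)^(n−1)
- More than one: P(>1) = 1 − P(0) − P(1)

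**n = 25, p = 0.05.** P(0) = 0.95^25 = 0.2774. P(1) = 25 × 0.05 × 0.95^24 = 1.25 × 0.2920 = 0.3650. P(>1) = 1 − 0.2774 − 0.3650 = 0.3576.

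**n = 25, p = 0.10.** P(0) = 0.90^25 = 0.0718. P(1) = 25 × 0.10 × 0.90^24 = 2.5 × 0.0798 = 0.1994 (before rounding the power). P(>1) = 1 − 0.0718 − 0.1994 = 0.7288.

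| Quantity | Rate | Section 11.2 | n = 25 | Stated minus correct (points) |
|---|---|---|---|---|
| Exactly one | 5% | 34% | 36.5% | −2.5 |
| More than one | 5% | 12% | 35.8% | −23.8 |
| Exactly one | 10% | 38% | 19.9% | +18.1 |
| More than one | 10% | 34% | 72.9% | −38.9 |
| At least one | 5% | 34 + 12 = 46% (implied) | 72.3% | −26.3 |
| At least one | 10% | 38 + 34 = 72% (implied) | 92.8% | −20.8 |
| None | 5% | 100 − 46 = 54% (implied) | 27.7% | +26.3 |
| None | 10% | 100 − 72 = 28% (implied) | 7.2% | +20.8 |

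One figure errs the other way: exactly one event at a 10% rate is overstated, because at n = 25 most of the probability has moved to two or more.

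**Reproducing the printed figures.** For every n from 1 to 200, the four probabilities were computed and rounded to whole per cent. Only n = 12 gives 34, 12, 38 and 34. Each scenario's pair taken alone also matches only n = 12.

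- p = 0.05: P(0) = 0.95^12 = 0.5404; P(1) = 12 × 0.05 × 0.95^11 = 0.3413; P(>1) = 0.1184.
- p = 0.10: P(0) = 0.90^12 = 0.2824; P(1) = 12 × 0.10 × 0.90^11 = 0.3766; P(>1) = 0.3410.

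**Other readings tried.** Pairs are in the order of the text.

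| Reading | 5% rate | 10% rate |
|---|---|---|
| Section 11.2 as printed | 34% / 12% | 38% / 34% |
| Poisson approximation, n = 25 | 35.8% / 35.5% | 20.5% / 71.3% |
| First figure as at least one, n = 25 | 72.3% / 35.8% | 92.8% / 72.9% |
| Second figure as more than two, n = 25 | 36.5% / 12.7% | 19.9% / 46.3% |
| Cohort of 24 | 36.9% / 33.9% | 21.3% / 70.8% |
| Cohort of 20 | 37.7% / 26.4% | 27.0% / 60.8% |
| Both cohorts pooled, n = 50 | 20.3% / 72.1% | 2.9% / 96.6% |

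None reproduces the text. The more-than-two reading comes near the 12% at a 5% rate, but it fails at a 10% rate, where the text itself says more than one. Reading the first figure as at least one matches no n from 2 to 100.

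**The case against.** The arithmetic is hard to dispute, so the case on the other side concerns weight and remedy.

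- **Little depends on the figures.** Section 11.2 promises only rough estimates, Section 11.3 is descriptive, the halting rules in Section 9.5 are triggered by specified events and use no probability, and Table 1 sets enrolment without reference to these percentages. This stands and limits the practical consequence. It does not excuse the figures: "rough" describes the precision of the safety estimates, whereas these probabilities follow exactly from n and p.
- **The direction is cautious.** A reader who trusts the text takes less reassurance from an event-free cohort than is warranted, not more. This stands as well, but the plan still misdescribes its own design.
- **The label may be wrong, not the numbers.** Because the percentages are those of 12 subjects and Table 1 has groups of up to 12, they may have been meant per age group. That is possible but only an inference; nothing in the document says so. The sentence says per cohort and Table 1 caps each cohort at 25, so recomputing for 25 is the sound repair.
- **The unit is loose.** The text counts AEs, while the binomial counts subjects with an AE, and a subject may receive up to three patches and have several events. This is fair and is best settled in the replacement wording.

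**Conclusion.** The concern holds. At the stated 25 subjects per cohort, the first figure is 2.5 points off and the other three are wrong by about 18 to 39 points. The chance of more than one event is 36% rather than 12% at a 5% rate, and 73% rather than 34% at 10%. The chance of at least one is 72% rather than 46%, and 93% rather than 72%. An event-free cohort of 25 would have a probability of 28% at a 5% rate and 7% at 10%, against the 54% and 28% that the text implies.

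This rests on independent subjects with a common event rate, and on a full cohort. Since 25 is a maximum, the values fall somewhat in a smaller cohort: between 20 and 25 subjects, the chance of more than one event runs from 26% to 36% at a 5% rate and from 61% to 73% at 10%. That does not bring them near the printed 12% and 34%.

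The text needs correcting because these are the plan's only stated detection probabilities and the design it names does not have them. The error does not alter enrolment, conduct or analysis.

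**What to change.** Replace the two scenario sentences in Section 11.2 with text such as:

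> With the maximum of 25 subjects in a cohort, if 5% of subjects truly experience the event, there is a 36% chance that exactly one subject has it and a 36% chance that more than one does. If the true rate is 10%, these chances are 20% and 73%.

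This corrects the four figures, marks 25 as a cap and makes the subject the unit. If the sponsor also wants figures for an age group of 12, the present percentages can stay in a separate sentence labelled as such.

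Optionally, and apart from the correction, the section could give the exact two-sided 95% upper limit when no event is seen in 25 subjects: 1 − 0.025^(1/25) = 13.7%.

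The cost is four numbers and a small rewording in one section. Enrolment, analyses and tables do not change.

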### 11.3 Analysis Plan

The safety population includes all subjects who receive the placebo microneedle patch. The safety population will be the primary analysis population for safety analyses. AEs will be analyzed using the safety population. Subjects will be analyzed as treated.

Primary Outcome Endpoints

AEs, reactogenicity events and SAEs will be recorded throughout the study. AEs will be coded using the Medical Dictionary for Regulatory Activities (MedDRA) dictionary. AE summary tables will be based on treatment-emergent AEs for the safety population. Descriptive statistics (e.g., number and percentage of subjects) will be used for each treatment group. AEs will be summarized by severity, relationship to treatment, and AEs leading to discontinuation. SAEs will also be tabulated by overall and treatment related events.

Secondary Outcome Endpoints

Unsolicited AEs and new-onset medical conditions (NOMC) will be recorded. AEs will be coded using the Medical Dictionary for Regulatory Activities (MedDRA) dictionary. AE summary tables will be based on treatment-emergent AEs for the safety population. Descriptive statistics (e.g., number and percentage of subjects) will be used for each treatment group. AEs will be summarized by severity, relationship to treatment, and AEs leading to discontinuation. NOMC will also be tabulated by overall and treatment related events.

## **12 ETHICS/PROTECTION OF HUMAN SUBJECTS**

### **12.1 Ethical Standard**

This study will be conducted in accordance with the protocol, the Declaration of Helsinki, ICH E6 GCP and local regulations.

### **12.2 Institutional Review Board**

Prior to initiating any study procedures, the Investigator will submit the following documents to the Emory IRB for review and approval: protocol and any amendments, informed consent, any documents to be given to the subject (e.g., memory aid), recruitment materials, and any other documents as requested by the IRB. A copy of the IRB approval will be submitted to the Sponsor.

Any amendments to the protocol or changes to the consent form must be submitted and approved by the IRB prior to implementation at the site. The Investigator will also ensure the timely dissemination of SAE and study safety reporting to the IRB in accordance with local IRB regulations and guidance.

### **12.3 Informed Consent Process**

Voluntary written informed consent must be obtained before any study-related procedures are performed in accordance with International Conference on Harmonization (ICH) guidelines and the requirements of informed consent (Title 21 Code of Federal Regulations (CFR) Parts 50.20 and 50.25). Consent must be documented by the use of a written consent form approved by the site's institutional review board (IRB) in accordance with Title 21 CFR Part 50.27.

Subject's LAR will be given an adequate amount of time to read the consent and ask any questions prior to signing the document. A copy of the signed informed consent will be provided to the subject LAR signing the form and the original retained in the source documents of the study subject.

## **12.4 Subject Confidentiality**

The investigational site participating in this study will maintain the highest degree of confidentiality for the clinical and research information obtained from the subjects in this clinical trial. Medical and research records will be maintained at each site in the strictest confidence. However, as a part of the quality assurance and legal responsibilities of an investigation, the investigational site will permit authorized representatives of FDA and health authorities to examine (and when required by applicable law, to copy) clinical records for the purpose of quality assurance reviews, audits, and evaluations of the study safety and progress. Unless required by the laws that permit copying of records, only the coded identity associated with documents or with other subject data may be copied (and all personally identifying information will be removed). Authorized representatives as noted above are bound to maintain the strict confidentiality of medical and research information that is linked to identify individuals.

A subject's privacy and confidentiality will be respected throughout the study. Each subject will be assigned a sequential identification number, and these numbers, rather than names, will be used during collection, storage, and reporting of subject information.

